8.3 Vital Signs

Vital signs will be measured as outlined in Appendix A.

Vital signs to be measured are listed below.

- Orthostatic systolic and diastolic BP and pulse rate
- Body temperature

- Respiratory rate

Blood pressure and pulse rate will be measured after the subject has been in the supine position for at least 5 minutes, repeat measurements will be taken after the subject has been standing in the upright position for at least 2 to 3 minutes (respiratory rate and temperature will be measured with blood pressure and pulse rate in the supine position only).

When vital signs are scheduled at the same time as PK blood draws, the blood draws will be obtained at the scheduled time point and the vital signs will be obtained prior to the blood draw, as close as possible to the scheduled time point.

On-study time points for vital sign measurements are presented in Table 9 (SAD Phase) and Table 10 (MAD Phase).

Table 9: Vital Sign Recording Schedule – SAD Phase

Vital Sign Recording - Scheduled Time Points¹
Upon admission (check-in)
Prior to dosing (within 60 minutes of dosing)
0.75, 1.25, 1.75, 3.75, 8, 11.75, and 23.25 hours post-dose (± 15 minutes)
Prior to discharge
End of Study/Follow-up Visit

¹For the food-effect cohort, the vital signs assessments will be performed for each dosing

Table 10: Vital Sign Recording Schedule – MAD and Smoker Phase

Vital Sign Recording - Scheduled Time Points
Upon admission (check-in)
Prior to dosing (within 60 minutes of dosing)
1.75 hours post-dose (± 15 minutes) on each dosing day
3.5 hours post-dose (± 15 minutes) on each dosing day ¹
Prior to discharge
End of Study/Follow-up Visit

¹ Time point applicable to Smoker Phase only.

The normal range values for vital signs are as follows:

- 100 mmHg \leq systolic blood pressure (BP) \leq 140 mmHg in supine position.
- 60 mmHg \leq diastolic BP \leq 90 mmHg in supine position.
- 60 beats per minute (bpm) \leq heart rate \leq 100 bpm in supine position.
- 35.5 °C \leq body temperature \leq 37.5 °C.
- 10 breaths per minute \leq respiratory rate \leq 22 breaths per minute.

- ≥ 20 mmHg decrease in systolic BP from supine to standing.
- ≥ 10 mmHg decrease in diastolic BP from supine to standing.
- ≥ 30 bpm increase in heart rate from supine to standing.

Actual values and change from baseline will be presented in a listing and will be summarized by study part, vital signs parameter, visit and time points. Values outside the reference range will be flagged in the listing.

Subject listing of abnormal on-study vital signs values (Out-of-Range) will be provided. Similarly, clinically significant on-study vital signs values will be presented in a second listing.

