Vital signs	Blood pressure, pulse, respiratory rate and body temperature	
Listings:
 
 • All vital signs values L16.2.8.3.1 – 16.2.8.3.2 • All out-of-range vital signs values • All clinically significant vital signs values T14.3.5.1.1 – T14.3.5.2.4 
Summary tables:
 
 • Summary of vital signs by visit T14.3.5.3.1 – T14.3.5.4.4
Physical examination	Physical examination findings	
Listings:
 
 • All Physical examination findings • L16.2.8.2 All clinically significant Physical Examination findings T14.3.6.1
Electrocardiograms (ECGs)	ECG interpretations and findings	
Listings:
 
 • all 12-Lead ECGs findings L16.2.8.4 
Summary tables:
 
 • summary of ECG assessments by visit • all out-of-range ECG values • all clinically significant ECG values T14.3.7.1.1 – T14.3.7.1.2 • all out-of-range ECG values T14.3.7.2.1 – T14.3.7.2.4
C-SSRS	Columbia Suicide Severity Rating Scale	
Listing:
 
L16.2.9.1

Note: Sub-bullets denote individual listings or tables to be generated.

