12 GENERAL INFORMATION RELATED TO DATA PRESENTATIONS

The formats and layouts of TFLs are provided in a separate document and are common displays. Their numbering and general content follow the International Conference on Harmonisation (ICH) E3 guidelines. Actual formats and layouts may be altered slightly from those presented as necessary to accommodate actual data or statistics. Minor format changes will not require updates to the SAP, rather they may be documented in a Note to SAP.

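### Three orthostatic abnormality criteria are listed as normal ranges in SAP 8.3 and Protocol 6.1.3, and no supine-to-standing variable is defined, so no valid orthostatic flag is specified

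*SAP*

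**What the plan says.** SAP Section 8.3 names "Orthostatic systolic and diastolic BP and pulse rate" among the vital signs to be measured and describes paired readings, supine and then standing. Under the words "The normal range values for vital signs are as follows" it gives eight items. Five are two-sided ranges: supine systolic pressure, supine diastolic pressure, supine heart rate, temperature and respiratory rate. The last three concern the change on standing. The first of these is at least a "20 mmHg decrease in systolic BP from supine to standing"; the others are a diastolic fall of at least 10 mmHg and a heart-rate rise of at least 30 bpm. Protocol Section 6.1.3 has the same list under the same heading.

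On the analysis, Section 8.3 says "Actual values and change from baseline will be presented in a listing", with summaries by study part, parameter, visit and time point. It adds "Values outside the reference range will be flagged in the listing". SAP Table 8 gives the vital-sign variables as "Blood pressure, pulse, respiratory rate and body temperature" and includes a listing of "All out-of-range vital signs values".

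Inclusion Criterion 10 (protocol synopsis and Section 4.1) contains the same three standing-change lines. There they define orthostatic hypotension and postural tachycardia, of which a subject must show no evidence at Screening.

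**The concern.** The same three lines cannot be both the normal range and the abnormality that Criterion 10 rules out. The label also has a use: the list in Section 8.3 is the only vital-sign range the SAP states, and the flag and the out-of-range listing depend on a range.

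The SAP text does not supply the variable that these lines would apply to. Change from baseline is measured against the last value before the first dose (SAP Section 9.3), so it is change over time and not change on standing.

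Changes in vital signs are part of the primary safety endpoint, and Protocol Section 1.4 counts orthostatic blood pressure and pulse among the monitoring practices it relies on. The paired data are collected without a valid stated rule for flagging them.

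**Working it through.** The documents state no figure to reproduce, so the check is a comparison of the two readings of the three lines.

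**Inputs.** Cut-offs of 20 mmHg (systolic fall), 10 mmHg (diastolic fall) and 30 bpm (heart-rate rise), identical in SAP 8.3, Protocol 6.1.3 and Criterion 10. Supine limits of 100–140 mmHg, 60–90 mmHg and 60–100 bpm, from the same list.

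**Rules.**
- Criterion 10 reading: a difference is abnormal when it meets the cut-off.
- Literal SAP 8.3 reading: meeting the cut-off is normal, so a difference is flagged when it does not meet the cut-off.

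**Results by size of change.**

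| Systolic fall / diastolic fall / heart-rate rise | Abnormal under Criterion 10 | Flagged under SAP 8.3 read literally |
|---|---|---|
| 0 / 0 / 0 | none | all three |
| 19 / 9 / 29 | none | all three |
| 20 / 5 / 10 | systolic | diastolic and heart rate |
| 20 / 10 / 30 | all three | none |

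The two rules are complements, so they disagree at every value. That follows from their form and is not an effect size. If a proportion *p* of differences truly meets a criterion, the literal rule flags 1 − *p*. The documents give no value for *p*; assumed values of 1% and 20% would give 99% and 80% flagged. Read literally, every subject who correctly satisfies Criterion 10 would be out of range on all three items at Screening.

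**If the three lines are ignored.** The remaining pressure and heart-rate limits are stated for the supine position, so they do not cover standing readings. Applying them to standing readings would not reliably help. Take an illustrative subject (not trial data) with supine 135/85 mmHg and pulse 62, and standing 110/72 mmHg and pulse 95:
- systolic fall 135 − 110 = 25, at least 20;
- diastolic fall 85 − 72 = 13, at least 10;
- pulse rise 95 − 62 = 33, at least 30.

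All three criteria are met, yet all six readings lie inside 100–140, 60–90 and 60–100. The supine limits raise no flag, and the literal rule raises none either.

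**The case against.** The strongest reply is that the two harms exclude each other. If the flag runs only on the variables in Table 8, the reversed lines are never applied and nothing is misflagged. If a difference is derived, the complaint about a missing variable largely falls. This is right as far as it goes: they are alternatives. But each leaves the trial without a valid orthostatic flag, reversed in one case and absent in the other.

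A second reply is that Criterion 10 also mixes five ranges and three abnormality definitions in one list, so the likely cause is a heading placed over a copied list, and a programmer would probably notice. The likely cause is accepted. The wording of Criterion 10 nevertheless makes the meaning of the three lines clear, whereas the heading in SAP 8.3 and Protocol 6.1.3 reverses it. The SAP is tied to the protocol version that contains Criterion 10 but does not repeat the criterion, so a correct flag requires departing from the SAP text.

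Third, Section 8.3 names the orthostatic readings and gives a direction and cut-off for each, so little is missing. That is fair, and it is why the repair is small. The derivation, the flag and the output still have to be stated.

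Fourth, Table 8 reserves two listing numbers for vital signs, and the SAP says of its outputs: "The formats and layouts of TFLs are provided in a separate document and are common displays". The shells might contain an orthostatic display. They were not available, so this stays open, and the conclusion is limited to the text of the protocol and SAP.

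Finally, the consequence is limited. Safety analysis is descriptive, and the vital-sign consideration for dose escalation in Protocol 3.5.2 turns on clinically significant abnormalities, not on this flag. That stands and bounds the point.

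**Conclusion.** The concern holds. Three of the eight items labelled as normal ranges are abnormality criteria, in both documents, and they contradict Criterion 10. The SAP text defines no supine-to-standing variable, so the stated rule yields either a reversed orthostatic flag or none.

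The effect is confined to the vital-sign flag and the out-of-range listing. Full listings, change-from-baseline summaries, the clinically significant listing and the escalation rules do not depend on it, and no data are lost. No number of misclassified subjects or readings is claimed.

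The conclusion rests on reading Criterion 10 in its evident sense and on the text alone, without the output shells. It should be fixed, because a reference-range rule feeding a primary safety output is wrong as written.

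**What to change.** Reconcile the passages:

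- In SAP 8.3 and Protocol 6.1.3, move the three lines out of the normal-range list and under a heading such as *criteria for abnormal orthostatic change*, keeping the documents' own thresholds. Criterion 10 needs no change.
- In SAP 8.3 and Table 8, state that supine-to-standing differences in systolic pressure, diastolic pressure and pulse are derived wherever both positions are measured, and are flagged and listed when a criterion is met.
- Check that the separate output shells follow the same rule.

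The cost is wording in two documents, three derived variables and one programming specification. No new data are needed, because both positions are already measured. The change should precede database lock and unblinding, since SAP Section 9 treats analyses performed after that point and not described in the plan as post hoc. The documents do not show whether lock has occurred.

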8.4 Physical Examination Findings

A physical examination will be performed by a medically qualified and licensed individual as outlined in Appendix A.

The physical examination will include a general review of the following body systems (at minimum): general appearance, head, eye, ear, nose, throat, neck/thyroid, cardiovascular, respiratory, gastrointestinal, neurological, musculoskeletal/extremities, and skin. An abbreviated physical examination may be performed at the Investigator's discretion upon admission or discharge from the clinical site.

All physical examination records will be presented in a listing, by study part, cohort, subject, visit and category. Similarly, clinically significant physical examinations will be presented in a second listing.

8.5 12-Lead ECG Findings

Triplet 12-lead ECG (each performed approximately 1 minute apart) will be performed as outlined in Appendix A.

On-study ECG measurements are specified in Table 11 (SAD Phase) and Table 12 (MAD Phase).

Table 11: ECG Recording Schedule – SAD Phase

ECG Recording - Scheduled Time Points¹
Upon admission (check-in)
Prior to dosing (within 60 minutes of dosing)
1, 3, 6, and 12 hours post-dose (± 15 minutes)
Prior to discharge
End of Study/Follow-up Visit

¹For the food-effect cohort, the vital signs assessments will be performed for each dosing

Table 12: ECG Recording Schedule – MAD and Smoker Phase

ECG Recording - Scheduled Time Point
Upon admission (check-in)
Prior to dosing (within 60 minutes of dosing) on Day 1 only
3 hours post-dose (± 15 minutes) on each dosing day
Prior to discharge
End of Study/Follow-up Visit

Mean values will be used for triplicate ECG results in summary tables. Actual values and change from baseline will be presented in a listing and will be summarized by study part, 12-Lead ECG parameter, visit and time point. Values outside the reference range will be flagged in a listing.

The 12-Lead ECG parameters and overall assessments (Normal, NCS, or Abnormal – CS) will be presented in a listing.

Subject listings of abnormal on-study ECG assessments (Abnormal – NCS or Abnormal – CS) will be provided. Similarly, clinically significant on-study 12-Lead ECG assessments (Abnormal – CS) will be presented in a second listing.

8.6 Columbia Suicide Severity Rating Scale (C-SSRS)

The C-SSRS is a questionnaire designed for the assessment of suicidal ideation and behavior in adolescents and adults. This will include events in the last 2 years prior to Screening.

To monitor for the emergence of suicidal ideation and behavior, subjects will undergo C-SSRS evaluations at the time points indicated in Appendix A.

On-study C-SSRS should be completed upon admission, upon discharge (each admission and discharge for Cohort A3 [Food-Effect Cohort]) and the EOS/Follow-up visit.

If a subject becomes suicidal during the study as per the results of the C-SSRS questionnaire, an Investigator should provide the appropriate treatment to the subject.

Listing will be presented for C-SSRS data.

9 DATA HANDLING AND PRESENTATION

All safety and statistical outputs will be generated using SAS software, version 9.4. Pharmacokinetic outputs will be generated using WinNonlin version 8.0.

All programs used to generate statistical analyses will be validated according to standard operating procedures (SOPs) of Altasciences.

The analyses described in this plan are considered a priori, in that they have been defined prior to database lock and/or prior to breaking the blind. Any analyses performed subsequent to database lock and/or breaking the blind that are not described within the present plan will be considered post hoc and exploratory. Post hoc analyses will be labeled as such in the corresponding statistical output and identified in the clinical study report (CSR).

9.1 Safety Analysis Presentation

Adverse events and medical history will be classified using the Medical Dictionary for Regulatory Activities (MedDRA) terminology version 24.0 as defined in the study data management plan (DMP).

Prior and concomitant medications will be coded with the World Health Organization Drug Dictionary- Enhanced (WHO-DDE) March 2021 as defined in the study DMP.

In general, all safety summary tables will be presented for the safety population. Summaries will be presented for each study part as below:

- Part A- SAD (Cohorts A1, A2, A3 fasted, A4, A5, Pooled Placebo and Overall)
- Part A food-effect cohort (SBP-9330, Placebo and Overall)
- Part B – MAD (Cohorts B1, B2, B3, B4, Pooled Placebo and Overall)
- Part C - Smoker (Cohorts C1, C2, C3, Pooled Placebo and Overall)

In general, the data listings will include all enrolled subjects up to the point of study completion or discontinuation; exceptions will be listings pertaining to a subset of subjects only (e.g., subjects with protocol deviations) or a subset of records/events (e.g., abnormal laboratory values).

Categorical variables will be summarized using the PROC FREQ procedure. Continuous variables will be summarized using the PROC UNIVARIATE procedure. For natural log (ln)-transformed endpoints, geometric mean, geometric standard deviation (SD), and coefficient of variation (CV%) will also be presented.

The following general comments also apply to all statistical analyses and data presentations:

- Duration variables will be calculated using the general formula: (end date - start date) +1.
- If the reported value of a clinical laboratory parameter cannot be used in a statistical summary table (e.g., a character string is reported for a parameter of the numerical type), a coded value must be appropriately determined and used in the statistical analyses. In general, a value or lower and upper limit of normal range such as ' <10 ' or ' ≤ 5 ' will be treated as '10' or '5' respectively, and a value such as ' >100 ' will be treated as '100'. However, the actual values as reported in the database will be presented in data listings.

- When assessments are repeated for a given time point or performed at unscheduled times, only the result which is the closest to the dosing time will be included in summary tables.

In general, summary statistics for raw variables (i.e., variables measured at the study site or central laboratory) will be displayed as follows:

- Minima and maxima will be displayed to the same number of decimal places as the raw data.
- Means, medians, and quartiles will be displayed to 1 additional decimal place.
- Standard deviations will be displayed to 2 additional decimal places.
- Percentages will be displayed to 1 decimal place. Percentages between 0 and 0.1 (exclusive) will be displayed as '<0.1'.
- P-values will be displayed to 3 decimal places. P-values that are less than 0.001 will be displayed as '<0.001'.

The numbers of decimal places for summary statistics of derived variables (i.e., variables that are not measured by the study site but are calculated for analysis based on other measured variables) will be determined on a case-by-case basis. In general:

- Minima and maxima will be displayed to the commonly used unit of precision for the parameter.
- Means, medians, quartiles, and confidence limits will be displayed to 1 additional decimal place.
- Standard deviations will be displayed to 2 additional decimal places.

9.2 Pharmacokinetic Analysis Presentation

In general, all PK summary tables will be presented for the PK population.

Individual raw PK concentrations will be displayed with the same precision as received from the bioanalytical laboratory.

Precision for individual PK parameters will be displayed as follows:

- Concentration-related PK parameters (e.g., C_{max} , AUCs) will be displayed to 3 significant figures,
- Clearance and volume of distribution will be displayed with 3 significant figures,
- Parameters associated with time (e.g. T_{max} and T_{half}) will be displayed with 2 decimal places,
- Percentages will be displayed with 2 decimal places,
- R^2 and λ_z will be displayed with 4 decimal places.

Summary statistics for concentration and PK parameters will be displayed with the same precision as the individual values, with the exception of number of observations (N) and CV% which will be presented with 0 and 1 decimal place, respectively.

9.3 Analysis Timepoints

Unless otherwise specified, the baseline value will be defined as the last non-missing evaluation prior to the first dose of study medication.

9.4 Methods for Handling Missing Data

No imputations of values for missing data (i.e, blank, “Not Done”, “Not Applicable”, etc) will be performed and data presentations will reflect the data point as it appears in the case report form (CRF) or electronic data file.

10 INTERIM ANALYSES AND DATA SAFETY MONITORING

Preliminary blinded “top line” PK results will be generated after each cohort of the SAD and MAD phase for dose selection and safety assessment prior to the next dose escalation.

These preliminary blinded PK results will be performed on SBP-9330 data as outlined in Sections 7.1 through 7.4, with the exception that nominal times will be used in the analysis instead of actual times. Blinded concentration tables, mean and blinded individual plasma concentration-time profiles, blinded PK parameter tables of the key PK endpoints (e.g., C_{max} , T_{max} , and AUCs) will be generated, data permitting.

11 CHANGES TO PROTOCOL-SPECIFIED ANALYSES

No changes from the protocol-specified analyses are planned.

12 GENERAL INFORMATION RELATED TO DATA PRESENTATIONS

The formats and layouts of TFLs are provided in a separate document and are common displays. Their numbering and general content follow the International Conference on Harmonisation (ICH) E3 guidelines. Actual formats and layouts may be altered slightly from those presented as necessary to accommodate actual data or statistics. Minor format changes will not require updates to the SAP, rather they may be documented in a Note to SAP.

APPENDIX A STUDY SCHEDULE(S)

Table 13: Schedule of Activities – Part A (SAD Phase with Nested Food-Effect Cohort)

Visit ²	Screening	Assessment Period ¹					Follow-up/ End of Study ³
		Pretreatment		Treatment			
Study Day	-28 to -2	-1	1 (Predose)	1	2	3	8±1
Confinement		X	X	X	X	X	
Ambulatory	X						X
Admission		X					
Discharge						X	
Informed Consent	X						
Eligibility Check	X	X	X				
Medical History	X	X					
Demographics	X						
Physical Examination	X	X ⁴				X ⁴	X
Body Weight and Height (Including BMI Calculation)	X	X ⁵					
Serology (HBsAg, HCVAb, anti-HIV 1 and 2)	X						
Urine Drug and Alcohol Screen ⁶	X	X					
FSH (postmenopausal females only)	X						
Pregnancy Test (Females Only) ⁷	X	X					X
Clinical Laboratory Tests ^{6,8}	X	X	X			X	X
12-lead ECG ^{9,10}	X	X	X	X		X	X
Vital Signs ^{10,11}	X	X	X	X	X	X	X
C-SSRS Questionnaire ¹²	X	X				X	X
M.I.N.I.	X						
Randomization		X					
Study Drug Administration				X			
Blood Sampling for PK ^{10,13}			X	X	X	X	
Previous and Concomitant Medication	X	X	X	X	X	X	X

Visit ²	Screening	Assessment Period ¹					Follow-up/ End of Study ³
		Pretreatment		Treatment			
Study Day	-28 to -2	-1	1 (Predose)	1	2	3	8±1
Adverse Event Monitoring		X	X	X	X	X	X

Abbreviations: BMI = body mass index; C-SSRS = Columbia-Suicide Severity Rating Scale; ECG = electrocardiogram; EOS = end of study; FSH = follicle-stimulating hormone; HBs Ag = hepatitis B surface antigen; HCVAb=hepatitis C virus antibody; HIV= human immunodeficiency virus; M.I.N.I. = Mini International Neuropsychiatric Interview; PK=pharmacokinetic; SAD = single ascending dose;

- 1 Subjects will be in the clinic from Day -1 until 48 hours (Day 3) post-dose. Subjects will return for follow-up/EOS assessments on Day 8±1. Subjects for the fed period of the food-effect cohort (Cohort A3) should report to the clinic after the washout period (at least 7 to 14 days after fasting dose) and repeat the 8-day SAD schedule of assessments beginning on Day -1.
- 2 The timing, type, and number of safety and PK assessments may be updated depending on emerging safety and PK data.
- 3 Subjects who discontinue the study early should complete the EOS procedures. Subjects in SAD cohorts A1, A2, A4, and A5 should return to the clinic for follow-up at Day 8±1; subjects in the food-effect 2-period cohort (Cohort A3) should return to the clinic for follow-up at Day 8±1 in Period 2 (5 days after the last PK blood sample in fed part).
- 4 An abbreviated physical examination may be performed at the Investigator's discretion upon admission and discharge from the clinical site.
- 5 Weight only.
- 6 Refer to Appendix 6 for more details.
- 7 Serum pregnancy test for all female subjects at Screening and urine pregnancy test, for female subjects of childbearing potential only, at all other timepoints.
- 8 Clinical laboratory tests (including clinical chemistry, lipid profile, coagulation, hematology, and urinalysis): at Screening; on Day -1 (admission) and at pre-dose, 48 hours post-dose; and at follow-up/EOS.
- 9 Triplicate 12-lead ECG: at Screening; Day -1 (admission), at pre-dose (within 60 minutes of dosing) and at 1, 3, 6, and 12 hours post-dose (±15 minutes); prior to discharge, and at follow-up/EOS.
- 10 When safety and PK blood draws coincide, procedures should be carried out in the following order: (1) ECGs, (2) vital signs, (3) PK blood sampling (nominal).
- 11 Vital signs: Screening; Day -1 (admission); at pre-dose (within 60 minutes of dosing) and at 0.75, 1.25, 1.75, 3.75, 8, 11.75, and 23.25 hours post-dose (±15 minutes); prior to discharge; and at follow-up/EOS. Orthostatic measurements will be obtained at Screening, Day -1, pre-dose, and at 1.75 hours (±15 minutes) post dose. For orthostatic measurements blood pressure and pulse rate will be measured after the subject has been in the supine position for at least 5 minutes, repeat measurements will be taken after the subject has been standing in the upright position for at least 2 to 3 minutes (respiratory rate and temperature will be measured with blood pressure and pulse rate in the supine position only).
- 12 A baseline/screening version of the C-SSRS will be used at Screening and a "since-last-visit" version will be used at all subsequent visits where the C-SSRS is administered.
- 13 Blood sampling for PK of SBP-9330 in plasma: at pre-dose (within 60 minutes of dosing) and 0.25, 0.5, 1, 1.5, 2, 3, 4, 6, 9, 12, 24, 36, and 48 hours post-dose (±10%).

Table 14: Schedule of Activities – Part B (MAD Phase)

Visit ¹	Screening	Assessment Period															Follow-up/ End of Study ²		
		Pretreatment		Treatment															
Study Day	-28 to -2	-1	1 (Predose)	2	3	4	5	6	7	8	9	10	11	12	13	14	15	16	21±1
Confinement		X	X	X	X	X	X	X	X	X	X	X	X	X	X	X	X	X	
Ambulatory ²	X																		X
Admission		X																	
Discharge																			X
Informed Consent	X																		
Medical History	X	X																	
Demographics	X																		
Physical Examination	X	X ³															X ³	X	
Body Weight and Height (Including BMI Calculation)	X	X ⁴																	
Serology (HBsAg, HCVAb, anti-HIV 1 and 2)	X																		
Urine Drug and Alcohol Screen ⁵	X	X																	
FSH (postmenopausal females only)	X																		
Pregnancy Test (Females Only) ⁶	X	X															X	X	
Clinical Laboratory Test ^{5,7}	X	X	X		X						X						X	X	X
12-lead ECG ^{8,9}	X	X	X	X	X	X	X	X	X	X	X	X	X	X	X	X	X	X	X
Vital Signs ^{9,10}	X	X	X	X	X	X	X	X	X	X	X	X	X	X	X	X	X	X	X
Eligibility Check	X	X																	
Randomization		X																	
Study Drug Administration				X	X	X	X	X	X	X	X	X	X	X	X	X	X	X	
Blood Sampling for PK ^{9,11}			X	X	X						X				X	X	X	X	X
C-SSRS Questionnaire ¹²	X	X															X		X
M.I.N.I.	X																		
Previous and Concomitant Medication	X	X	X	X	X	X	X	X	X	X	X	X	X	X	X	X	X	X	X

Visit ¹	Screening	Assessment Period														Follow-up/ End of Study ²			
		Pretreatment		Treatment															
Study Day	-28 to -2	-1	1 (Predose)	2	3	4	5	6	7	8	9	10	11	12	13	14	15	16	21±1
Adverse Event Monitoring		X	X	X	X	X	X	X	X	X	X	X	X	X	X	X	X	X	

Abbreviations: BMI = body mass index; C-SSRS = Columbia-Suicide Severity Rating Scale; ECG = electrocardiogram; EOS = end of study; FSH = follicle-stimulating hormone; HBsAg = hepatitis B surface antigen; HCVAb = hepatitis C virus antibody; HIV = human immunodeficiency virus; MAD = multiple ascending dose; M.I.N.I. = Mini International Neuropsychiatric Interview; PK = pharmacokinetic

- 1 The timing, type, and number of safety, and PK assessments may be updated depending on emerging safety and PK data.
- 2 Subjects who discontinue the study early should complete the EOS procedures.
- 3 An abbreviated physical examination may be performed at the Investigator's discretion upon admission or discharge from the clinical site.
- 4 Weight only.
- 5 Refer to Appendix 6 for more details.
- 6 Serum pregnancy test for all female subjects at Screening and urine pregnancy test, for female subjects of childbearing potential only, at all other timepoints.
- 7 Clinical laboratory tests (including clinical chemistry, lipid profile, coagulation, hematology, and urinalysis): at Screening; on Day -1 (admission); at pre-dose on Days 1, 3, 7, 14, and 16; and at follow-up/EOS.
- 8 Triplicate 12-lead ECG: at Screening; Day -1 (admission); at pre-dose (within 60 minutes) on Day 1 and at 3 hours post-dose on each dosing day (i.e., Days 1 to 14) (±15 minutes); prior to discharge; and at follow-up/EOS.
- 9 When safety and PK blood draws coincide, procedures should be carried out in the following order: (1) ECGs, (2) vital signs, (3) PK blood sampling (nominal).
- 10 Vital signs: at Screening; Day -1 (admission); at pre-dose (within 60 minutes) and 1.75 hours post-dose on each dosing day (i.e., Days 1 to 14) (±15 minutes); prior to discharge; and at follow-up/EOS. Orthostatic measurements will be obtained at Screening, Day -1, pre-dose, and at 1.75 hours (±15 minutes) post dose. For orthostatic measurements blood pressure and pulse rate will be measured after the subject has been in the supine position for at least 5 minutes, repeat measurements will be taken after the subject has been standing in the upright position for at least 2 to 3 minutes (respiratory rate and temperature will be measured with blood pressure and pulse rate in the supine position only).
- 11 Blood sampling for PK of SBP-9330 in plasma: at pre-dose (within 60 minutes of dosing); at 0.25, 0.5, 1, 1.5, 2, 3, 4, 6, 9, 12, and 24 hours post-dose (±10%) on Day 1; within 60 minutes prior to morning drug administration on Day 7, 11, 12, and 13; and within 60 minutes prior to drug administration and at 0.25, 0.5, 1, 1.5, 2, 3, 4, 6, 9, 12, 24, 36, and 48 hours post-dose on Day 14 (±10%).
- 12 A baseline/screening version of the C-SSRS will be used at Screening and a "since-last-visit" version will be used at all subsequent visits where the C-SSRS is administered.

Table 15: Schedule of Activities – Part C (Smoker Phase)

Visit ¹	Screening	Assessment Period															Followup/ End of Study ²		
		Pretreatment		Treatment															
Study Day	-28 to -2	-1	1 (Predose)	2	3	4	5	6	7	8	9	10	11	12	13	14	15	16	21±1
Confinement		X	X	X	X	X	X	X	X	X	X	X	X	X	X	X	X	X	
Ambulatory ²	X																		X
Admission		X																	
Discharge																			X
Informed Consent	X																		
Medical and Smoking History	X	X																	
Demographics	X																		
Physical Examination	X	X ³															X ³	X	
Body Weight and Height (Including BMI Calculation)	X	X ⁴																	
Serology (HBsAg, HCVAb, antiHIV 1 and 2)	X																		
Urine Drug and Alcohol Screen ⁵	X	X																	
FSH (postmenopausal females only)	X																		
Pregnancy Test (Females Only) ⁶	X	X															X	X	
Clinical Laboratory Test ^{5,7}	X	X	X		X				X				X				X	X	X
12-lead ECG ^{8,9}	X	X	X	X	X	X	X	X	X	X	X	X	X	X	X	X	X	X	
Vital Signs ^{9,10}	X	X	X	X	X	X	X	X	X	X	X	X	X	X	X	X	X	X	
Eligibility Check	X	X																	
Randomization		X																	
Study Drug Administration				X	X	X	X	X	X	X	X	X	X	X	X	X	X	X	
Blood Sampling for PK ^{9,11}			X	X	X					X			X	X	X	X	X	X	
Expired CO Level ¹²	X	X	X	X	X	X	X	X	X	X	X	X	X	X	X	X	X	X	
Blood Sampling for Cotinine ¹³			X						X								X		
Smoking Log		X		X	X	X	X	X	X	X	X	X	X	X	X	X	X	X	

Visit ¹	Screening	Assessment Period															Followup/ End of Study ²		
		Pretreatment		Treatment															
Study Day	-28 to -2	-1	1 (Predose)	2	3	4	5	6	7	8	9	10	11	12	13	14	15	16	21±1
FTCD		X																	
Smoking TLFB	X	X																	
MNWS		X		X	X	X	X	X	X	X	X	X	X	X	X	X	X		
QSU-Brief		X		X	X	X	X	X	X	X	X	X	X	X	X	X	X		
C-SSRS Questionnaire ¹⁴	X	X															X		X
M.I.N.I.	X																		
Previous and Concomitant Medication	X	X	X	X	X	X	X	X	X	X	X	X	X	X	X	X	X	X	X
Adverse Event Monitoring		X	X	X	X	X	X	X	X	X	X	X	X	X	X	X	X	X	X

Abbreviations: BMI = body mass index; C-SSRS = Columbia-Suicide Severity Rating Scale; CO = carbon monoxide; ECG = electrocardiogram; EOS = end of study; FSH = follicle-stimulating hormone; FTCD = Fagerström Test for Cigarette Dependence; HBsAg = hepatitis B surface antigen; HCVAb = hepatitis C virus antibody; HIV = human immunodeficiency virus; MAD = multiple ascending dose; M.I.N.I. = Mini International Neuropsychiatric Interview; MNWS = Modified Minnesota Nicotine Withdrawal Scale; PK = pharmacokinetic; QSU-Brief = Questionnaire on Smoking Urges – Brief version; TLFB = Smoking Time-Line Follow-back

1. The timing, type, and number of safety, and PK assessments may be updated depending on emerging safety and PK data.

2. Subjects who discontinue the study early should complete the EOS procedures.

3. An abbreviated physical examination may be performed at the Investigator's discretion upon admission or discharge from the clinical site.

4. Weight only.

5. See APPENDIX 6 from protocol for details.
6. Serum pregnancy test for all female subjects at Screening and urine pregnancy test, for female subjects of childbearing potential only, at all other timepoints.
7. Clinical laboratory tests (including clinical chemistry, lipid profile, coagulation, hematology, and urinalysis): at Screening; on Day -1 (admission); at pre-dose on Days 1, 3, 7, 14, and 16; and at follow-up/EOS.
8. Triplicate 12-lead ECG: at Screening; Day -1 (admission); at pre-dose (within 60 minutes) on Day 1 and at 3 hours post-dose on each dosing day (i.e., Days 1 to 14) (± 15 minutes); prior to discharge; and at follow-up/EOS.
9. When safety and PK blood draws coincide, procedures should be carried out in the following order: (1) ECGs, (2) vital signs, (3) PK blood sampling (nominal), (4) smoking assessments.
10. Vital signs: at Screening; Day -1 (admission); at pre-dose (within 60 minutes) and 1.75 hours post-dose on each dosing day (i.e., Days 1 to 14) (± 15 minutes); prior to discharge; and at follow-up/EOS. Orthostatic measurements will be obtained at Screening, Day -1, pre-dose, 1.75 hours (± 15 minutes), and 3.5 hours (± 15 minutes) post dose. For orthostatic measurements blood pressure and pulse rate will be measured after the subject has been in the supine position for at least 5 minutes, repeat measurements will be taken after the subject has been standing in the upright position for at least 2 to 3 minutes (respiratory rate and temperature will be measured with blood pressure and pulse rate in the supine position only).
11. Blood sampling for PK of SBP-9330 in plasma: at pre-dose (within 60 minutes of dosing); at 0.25, 0.5, 1, 1.5, 2, 3, 4, 6, 9, 12, and 24 hours post-dose ($\pm 10\%$) on Day 1; within 60 minutes prior to morning drug administration on Day 7, 11, 12, and 13; and within 60 minutes prior to drug administration and at 0.25, 0.5, 1, 1.5, 2, 3, 4, 6, 9, 12, 24, 36, and 48 hours post-dose on Day 14 ($\pm 10\%$).
12. Expired breath CO will be measured with a Bedfont Smokerlyzer™.
13. Cotinine samples should be collected within 60-minutes prior to dosing on dosing days.
14. A baseline/screening version of the C-SSRS will be used at Screening and a “since-last-visit” version will be used at all subsequent visits where the C-SSRS is administered.
